Awake prone positioning and oxygen therapy in patients with COVID-19 (APRONOX)

*Prospective, observational, multicenter study.* 

Identifiers: NCT04407468 Unique Protocol ID: 1178/SESEQ-HSGJR/08-05- 20/UTI Date: 10/05/2020

APRONOX trial is a retrospective, observational, multicenter study that consists of the main objective, which is to observe the impact of the awake prone, and to see how many patients required intubation, with the additional objectives described in this research

By the APRONOX group

# Awake prone positioning and oxygen therapy in patients with COVID-19 (APRONOX)

Prospective, observational, multicenter study.

# Identifiers: NCT04407468 Unique Protocol ID: 1178/SESEQ-HSGJR/08-05- 20/UTI

# Theoretical framework

The prone position strategy for patients with acute respiratory distress syndrome (ARDS) is simple and cost-effective since the first description on its use in patients with acute respiratory failure to improve hypoxemia. Different studies have looked for its safety and efficacy in various clinical scenarios, demonstrating that its early use in combination with non-invasive mechanical ventilation (NIV) or high-flow oxygen therapy can reduce intubation rate and mortality in ARDS. In the COVID-19 pandemic, high-value medicine and resource optimization are critical.

Scaravilli et al (1) carried out an analysis of 15 patients admitted presenting acute hypoxemic respiratory failure with spontaneous breathing undergoing a prone position, finding that the strategy had no deleterious effects on PaCO2, pH, respiratory rate, or hemodynamics. For their part, Valter et al (2) reported four cases of patients with respiratory failure where a prone position strategy was used, showing an improvement in oxygenation and good tolerance while awake, avoiding the need for intubation in these patients without significant complications (2).

Ding et al (3) recently published a prospective cohort study of patients with moderate to severe grade ARDS using the prone position combined with non-invasive mechanical ventilation (NIV) or high flow nasal cannula (HFNC), demonstrating the safety and efficiency of the maneuver, finding an improvement in oxygenation and a decrease in the need for intubation. Pérez et al (4) reported a case series of patients with severe non-infectious ARDS where the strategy of early prone and HFNC or NIV, for 2 to 3 hours, improved oxygenation and intubation was avoided in 5 of the 6 cases studied.

Sun et al (5), perform an early intervention strategy in patients with coronavirus-2019 disease (COVID-19) and respiratory failure, supported by NIV or HFNC using the awake prone positioning, reporting a low intubation rate and mortality compared to other regions of China affected by the SARS-CoV-2. Caputo et al (6) evaluated an early awake prone positioning in patients with COVID-19 in an emergency service; describing 50 cases with an oxygen saturation on admission <90%, after the early awake prone strategy for 30-120 minutes, oxygenation improved and intubation was avoided in 64% of patients. Slessarev et al (7), analyzed a patient with COVID-19-associated pneumonia, who was treated with high-flow nasal cannula and awake prone positioning, allowing him to interact with family members and participate in active physiotherapy, the primary result showed an improvement in oxygenation.

There are currently studies in progress to evaluate the benefit of the prone position in patients with COVID-19. The APPROVE-CARE-2020 study is an open, randomized, multicenter controlled study of acute hypoxemic respiratory failure or COVID-19-induced respiratory distress syndrome

seeking to determine whether the prone position awake reduces the need for mechanical ventilation (8). The OPTIPRONE clinical trial is recruiting patients with the objective of monitoring the PaO2 / FiO2 ratio with a strategy based on prone position and high-flow oxygen therapy over a period of 2 hours, the current status is awaiting for reporting results (9).

The awake prone position can be combined with a variety of non-invasive oxygenation strategies. The evidence documented so far has shown that it is a safe and effective strategy, and it has been observed that performing it early has been associated with benefit in survival and reduction of the intubation rate in patients with moderate and severe respiratory failure. Another advantage of this technique is that the awake prone position can be performed even in atmospheric air in emergency situations, or in contexts of limited resources. This strategy aims to be a safe, dynamic, practical and free strategy at any level of health care (3). For the diagnosis of COVID-19, reverse transcriptase polymerase chain reaction (RT-PCR) is considered the standard test. However, there are limitations such as the shortage of kits, limitations in sampling and transportation that can give us cases of false negatives in the early stages of the disease. For this reason, imaging studies such as chest tomography (CT) can be a valuable diagnostic method in patients with suspected covid-19 disease, a sensitivity of up to 97% has been observed (10-12).

Shang Wan (11) performed a meta-analysis where 1115 patients were included, where chest tomography images were observed, in which the following characteristics and image patterns were observed:

- 1. Ground glass opacities and pleural thickening (69%)
- 2. Peripheral distribution (70%)
- 3. Consolidation (47%)
- 4. Air bronchogram (46%)
- 5. Involvement of the right lower lobe (70%)
- 6. Involvement of more than 3 lobes (70%)
- 7. Crazy paving pattern (15%)

In particular, a full understanding of the patterns on tomography as well as the clinical features may be beneficial for an effective diagnosis and treatment in patients with COVID-19 infection (11).

#### **Problem statement**

The first case of COVID-19 in Mexico was reported on February 27, 2020, currently our country has 27.2 cases per 100,000 habitants. According to the Ministry of Health, there are currently 36,327 confirmed cases of COVID-19 in the country with a total of 3,573 deaths. The WHO reports in the month of May, Mexico presented a case fatality rate (CFR) of 12%, being one of the highest reported during the SARS-COV 2 pandemic. COVID-19 has a wide range of clinical manifestations, ranging from asymptomatic to severe ARDS that requires invasive mechanical ventilation. According to Chinese reports, not all severe cases of COVID-19 required admission to the ICU, in Italy 12% of positive patients required admission to the critical care unit. In Mexico it has been observed that 56% of the patients who required intubation for severe management of the disease die, on the other hand, in China, 49% of the patients with a severe picture of COVID-19 died. In a multicenter study during the early outbreak in Wuhan 97% of the patients who required invasive mechanical ventilation died, although mortality could be affected by medical practice in each region. It seems important to highlight that several patients who require intubation are in a high risk of dying. There are some comorbidities related to an increased mortality such as hypertension, diabetes, vascular diseases, COPD and cancer, highly prevalent diseases in the Mexican environment. Mortality in patients with mechanical ventilation is striking, it makes us wonder if the ventilatory management per se generates complications that lead the patient to death, such as Ventilator-Induced Lung Injury (VILI), hemodynamic repercussion due to positive pressure or the fact that intubated patients are simply more critically ill patients. Another current issue that has been observed internationally is the lack of medical equipment due to the high demand for patients. One of the strategies that have been reproduced internationally is the placement of prone patients early in awake patients without mechanical ventilation, with encouraging preliminary results.

#### **Research question**

In patients diagnosed with COVID-19 infection. What is the relationship between the awaken prone position and the need for orotracheal intubation?

#### Justification

COVID-19 is a pandemic that has significantly challenged health systems worldwide. Due to the large number of infections around the world, the implementation of strategies to reduce the number of intubations and the need for invasive mechanical ventilation becomes important. In addition to the inability of the Mexican health system to respond, patients under invasive ventilation have not had a favorable survival outcome. Up to 97% mortality has been reported in patients requiring intubation. The exact cause of this poor prognosis is not yet known. Early recognition of hypoxemic patients could help with the results. It seems reasonable in these patients to perform procedures to improve the clinical respiratory picture before intubation in less severe cases due to the quoted above. Prone patient placement during invasive mechanical ventilation is a widespread practice in the management of severe ARDS of other etiologies. Currently, few attempts have been made to implement the prone position in patients who spontaneously ventilate with supplemental oxygen, high-flow nasal cannulas, or noninvasive mechanical ventilation. Taking into account that it is a procedure that does not require additional infrastructure within the services and does not represent an additional cost for its implementation, it becomes a valuable tool in the context of COVID-19 where intubation is associated with high mortality, additionally there are mechanical ventilator deficits in most hospitals. This work has feasibility to be carried out because it will be carried out in critical areas that have equipment and trained personnel for it in the different shifts, in addition to having patients diagnosed with COVID-19.

**Null hypothesis (H0):** In patients diagnosed with COVID-19 infection, there is no relationship between the awaken prone positioning and orotracheal intubation.

Alternate hypothesis (H1): In patients diagnosed with COVID-19 infection, there is a relationship between the awaken prone positioning and the need for orotracheal intubation.

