#### Methodology

Study type: Observational, retrospective cohort study.

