#### **Inclusion criteria**

Patient's records with the following characteristics:

- Patients over 18 years of age
- Patients of both genders
- Patients diagnosed with COVID-19 infection
- Patients admitted to hospital
- Complete file

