#### Dependent

Variable	Conceptual definition	Operational definition	Туре	Measurement scale
Orotracheal intubation	Placing a probe into the trachea through the mouth or nose to connect to a mechanical ventilator.	Performing intubation for any cause or non- intubation during your hospitalization.	Qualitative	Nominal (dichotomous): Yes No

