# Independent variable

Variable	Conceptual definition	Operational definition	Туре	Measurement scale (years)	
Age	Time elapsed from the birth of a person to a certain moment.	The age recorded in the clinical record at the patient's admission to the hospital will be considered.	Discrete quantitative	
 
18 a 27
 
28 a 37
 
38 a 47
 
48 a 57
 
58 a 67
 
68 a 77
 
78 a 87
 
88 a 97
 
997
 
	
Gender	Social concepts of functions, behaviors, activities and attributes for men and women.	Gender that is registered in the clinical record	Qualitative nominal	Male Female	
Prone position	What is called the prone position	Record in the record of the placement of the patient in the prone position for a minimum of 2 hours.	Qualitative	Nominal (dichotomous): Yes No	
Type of oxygen support supplied	Device used for supplemental oxygen administration.	Record in the clinical record of the type of oxygen supplied.	Qualitative nominal	
 
Nasal cannulas
 
High flow nasal cannulas
 
Face mask
 
Other
 
	
Partial oxygen saturation index (SpO2) / inspired oxygen fraction (FiO2)	Resulting index for SpO2 / FiO2 ratio	2 index records will be taken at admission and the second after the patient's prone position, recorded in the clinical record.	Discrete quantitative	1. 100 a 150 2. 151 a 200 3. 201 a 250 4. 251 a 300 5. 301 a 350	

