# Confusing variables

Variable	Conceptual definition	Operational definition	Туре	Measurement scale
Comorbidities	Presence of one or more disorders in addition to the primary disease or disorder	Registration in the clinical record of any of the comorbidities described.	Qualitative nominal	
 
1 Diabetes mellitus
 
2 Systemic arterial hypertension
 
3 Chronic obstructive pulmonary disease
 
4 Obesity
 
5 Chronic kidney disease
 
6 Ischemic heart disease
 
7 Other heart diseases
 
8 Other diseases
 

Pharmacotherapy		Registration in the clinical record of the described management.	Qualitative nominal	
 
Antivirals
 
Hydroxychloroquine
 
Antibiotics
 
Corticosteroids
 
Immunomodulators
 
Others
 

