#### Information gathering instrument

Case	Gender	Age	Comorbidities	Type of oxygen support supplied	Pharmacotherapy	Awake prone position (Yes/no)	Time of Awake prone position (hours)	Initial SaO2/FiO2	SaO2/FiO2 before to the prone position	Prone position (hours)	Intubation Yes/No

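### Admission date is neither collected nor accounted for, so a calendar-time trend of unknown size and direction could appear as an effect of awake proning on intubation

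*Protocol*

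**What the plan says.** The Methodology section gives the design as "Study type: Observational, retrospective cohort study", although the title page also calls the study prospective. The Inclusion criteria require adults with a COVID-19 diagnosis, a complete file and "Patients admitted to hospital". They give no range of admission dates.

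The exposure is a yes/no variable: "Record in the record of the placement of the patient in the prone position for a minimum of 2 hours". The outcome is also yes/no: "Performing intubation for any cause or non- intubation during your hospitalization". Neither is tied to a calendar date. The table of confounders has two entries, comorbidities ("Registration in the clinical record of any of the comorbidities described") and pharmacotherapy.

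The Information gathering instrument has 12 columns. Its only time fields are durations, namely "Time of Awake prone position (hours)" and a second column for hours prone. No column holds a date.

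The Statistical analysis section tests intubation against prone position with a chi-square or Fisher exact test and reports a relative risk, all unadjusted. The regression that follows names prone time, age, gender, intubation and SpO2/FiO2. Calendar period is not in it.

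On context, the Justification describes awake proning as little tried so far ("Currently, few attempts have been made to implement the prone position in patients who spontaneously ventilate with supplemental oxygen") and adds "additionally there are mechanical ventilator deficits in most hospitals".

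**The concern.** A variable confounds this comparison if it is related to both prone use and intubation. The protocol's own background gives reasons to expect that of calendar time.

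- **Exposure.** Awake proning was uncommon when the protocol was written. The Problem statement calls the early results encouraging, and the Ethical considerations section gives wider adoption as an aim. Rising uptake would be unsurprising.
- **Outcome.** The Problem statement dates Mexico's first case to 27 February 2020 and, in a protocol of May 2020, counts 36,327 confirmed cases. It attributes equipment shortage to high demand. It also asks whether ventilation itself harms patients, and the Justification finds it reasonable to try other measures before intubation in less severe cases. Ventilator supply and the threshold for intubation both bear directly on whether a patient is intubated.

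If both moved over the months covered, the prone and non-prone groups would differ in when their patients were admitted, and the relative risk would partly compare periods. This can happen inside one hospital, so adjusting for centre would not remove it. Analysts holding only the planned dataset could neither see such a trend nor adjust for it.

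**Working it through.** **1. The plan's own figure.** The sample size section uses N = 8463, Z = 1.96, p = q = 0.5 and E = 0.05:

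n = N Z² p q / [(N − 1) E² + Z² p q] = 8463 × 0.9604 / (8462 × 0.0025 + 0.9604) = 8127.87 / 22.1154 = 367.52, rounded up to 368.

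The stated 368 reproduces. It does not depend on this point and is used below only as the total sample size.

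**2. Illustration of the bias.** The documents give no rates by period, so every period rate here is an assumption. Take two calendar periods with equal numbers of patients, prone uptake u1 then u2, and intubation risk r1 then r2. Within each period the risk is the same for prone and non-prone patients, so the true relative risk is 1.

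- Crude risk, prone: P = (u1 r1 + u2 r2) / (u1 + u2)
- Crude risk, non-prone: Q = [(1 − u1) r1 + (1 − u2) r2] / (2 − u1 − u2)
- Crude RR = P / Q

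In the first case, P = 0.2 × 0.50 + 0.8 × 0.30 = 0.34 and Q = 0.8 × 0.50 + 0.2 × 0.30 = 0.46, so RR = 0.74.

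The last column is the probability that the unadjusted two-sided test at 0.05 rejects with 368 patients (normal approximation): Φ[(d − 1.96 s0)/s1] + Φ[(−d − 1.96 s0)/s1]. Here d = P − Q, s0 is the pooled standard error and s1 the unpooled one. In the first case d = −0.12, s0 = 0.0511 and s1 = 0.0507, which gives Φ(0.39) = 0.65; the other tail is negligible.

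| Uptake | Intubation risk | P | Q | Crude RR | Rejects |
|---|---|---|---|---|---|
| 20% → 80% | 50% → 30% | 0.34 | 0.46 | 0.74 | 65% |
| 30% → 70% | 50% → 30% | 0.36 | 0.44 | 0.82 | 35% |
| 30% → 70% | 45% → 35% | 0.38 | 0.42 | 0.90 | 12% |
| 40% → 60% | 40% → 30% | 0.34 | 0.36 | 0.94 | 7% |
| 20% → 80% | 30% → 50% | 0.46 | 0.34 | 1.35 | 65% |
| 20% → 80% | 40% → 40% | 0.40 | 0.40 | 1.00 | 5% |
| 50% → 50% | 50% → 30% | 0.40 | 0.40 | 1.00 | 5% |

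The last two rows show that both uptake and risk must change for any bias to arise. In every row, stratifying by period returns a relative risk of 1, because the two groups have equal risk within each period.

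**3. Unequal periods.** In a growing epidemic most patients may fall in the later period. With 80% there (assumed):

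- Strong case: P = (0.04 × 0.50 + 0.64 × 0.30) / 0.68 = 0.312 and Q = (0.16 × 0.50 + 0.16 × 0.30) / 0.32 = 0.400, so RR = 0.78.
- Milder case (30% → 70%; 45% → 35%): P = (0.06 × 0.45 + 0.56 × 0.35) / 0.62 = 0.360 and Q = (0.14 × 0.45 + 0.24 × 0.35) / 0.38 = 0.387, so RR = 0.93.

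The bias shrinks but does not vanish.

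**The case against.** Several stronger readings are tempting, and the documents do not support them.

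- **That proning and ventilator supply were both changing during the study.** The protocol defines no study period and reports no trend in either. Its remarks on few attempts and on ventilator deficits are in the present tense. The first may describe the method's general use rather than uptake at the participating hospitals.
- **That ventilator shortage drove intubation at these sites.** Just after mentioning the deficits, the Justification says that the study areas have the equipment and trained staff needed. The shortage is general and is not stated for the sites.
- **That the prone group is late and the control group early.** This is a conjecture about uptake, not something the text shows.
- **That the bias favours proning.** That requires uptake and intubation risk to move in opposite directions. If both rose, for example because later admissions were sicker, the bias would run towards harm.
- **That the gap cannot be repaired.** The source of all variables is the clinical file, so the date could be abstracted later.

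It can also be said that covariate choice is often left to the analysis plan, that the main test is unadjusted for everything, and that the regression omits even the listed confounders. All of that is fair, and calendar time is one confounder among several. But the form is part of the protocol, and no analysis plan can use a date that was not abstracted without returning to the files. That part of the point stands, as does the missing admission window.

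**Conclusion.** The point holds as a possible confounder of unknown size and direction. What the text establishes is that there is no admission window, no date on the form and no account of calendar period in the analysis. That prone use and intubation risk changed over time is a reasonable inference from the background sections, not a documented fact.

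The relative risks above show what could happen, not what did. They rest wholly on assumed period rates, two periods and no true effect. Strong trends would seriously mislead the planned test, while mild ones would hardly matter. The protocol gives no basis for choosing between these cases, and the planned data would give none either. That is reason enough to record the date. The sample size of 368 is unaffected.

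**What to change.** 1. State the range of admission dates in the Inclusion criteria.
2. Add date of admission to the Information gathering instrument and to the variable tables. Week of admission would be enough if exact dates raise a confidentiality concern.
3. In Statistical analysis, adjust or stratify the prone–intubation comparison by calendar period (for example two-week blocks), alongside the other confounders.
4. Tabulate prone use and intubation risk by period, so that readers can see whether either moved.

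The cost is one column from a file that is being opened anyway; if abstraction has begun, those files must be revisited. The confidence interval also widens. With two equal periods, uptake u and 1 − u, and roughly constant outcome variance, the factor is about √[0.25 / (u(1 − u))]. That is √(0.25/0.24) = 1.02 for 40% → 60%, √(0.25/0.21) = 1.09 for 30% → 70%, and √(0.25/0.16) = 1.25 for 20% → 80%. The loss is slight unless uptake changed sharply, which is when the adjustment is most needed.

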# Objective

#### Main objective

To analyze the relationship between the awaken prone positioning and the need for orotracheal intubation.

# **Specific objectives**

To explore the impact of the awaken prone positioning on the partial oxygen saturation / inspired oxygen fraction index (SaO2 / FiO2).

Determine the free hours without the need for orotracheal intubation of patients in the awaken prone positioning.

To describe the characteristics of the patients in need of orotracheal intubation who were in the awaken prone positioning and those who were not.

#### Methodology

Study type: Observational, retrospective cohort study.

#### **Study characteristics**

- Based on an intervention or not for research purposes: Observational.
- For follow up or not of patients over time: Longitudinal
- For directionality in obtaining information: **Retrospective**
- By the search or not of associations between two variables: Comparative
- By type of population: Homodemic, multicenter.

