#### Statistical analysis

Descriptive statistics, measures of central tendency, measures of dispersion and standard deviation will be used.

While for the qualitative variable's frequency measures (relative, absolute and percentage) were used. Relative risk will be performed with a 95% confidence interval of significance (95% CI) and contingency tables.

For inferential statistics, the difference in proportions between the dependent (orotracheal intubation) and independent (prone position) variables will first be verified based on the number of expected observations (<5) Fisher's exact test or (> 5) Chi square test, contrasting H0:  $\phi = 1$ , taking p <0.05 as a statistically significant value.

A multivariate analysis will be used to generate linear regression models with the different variables: prone time, age, gender and orotracheal intubation, SpO2 / FiO2 index in order to explain their interactions (if the time in prone, age or gender affects the main objective) as well as adopting the best model that matches the observations (best R2, AIC) as a predictive model.

The results will be presented in graphs and / or tables as appropriate.

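### The study is multicentre, but the main prone-by-intubation comparison is one pooled, unstratified table and centre is neither a listed variable nor a field on the form, so differences in local practice can be read as a prone effect

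*Protocol*

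**What the plan says.** Protocol, Methodology: "Study type: Observational, retrospective cohort study". Protocol, Study characteristics, on the type of population: "Homodemic, multicenter". Exposure is therefore whatever the treating hospital did. It is not allocated by the study.

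Protocol, Statistical analysis: "the difference in proportions between the dependent (orotracheal intubation) and independent (prone position) variables will first be verified", by Fisher's exact test or chi-square depending on expected counts, at p < 0.05. The effect measure comes from the same tables: "Relative risk will be performed with a 95% confidence interval of significance (95% CI) and contingency tables". No stratification is mentioned. The regression that follows lists prone time, age, gender, intubation and the SpO2/FiO2 index.

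Centre is missing from four places where it could have stood:

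- the independent-variable table (age, gender, prone position, oxygen support, SpO2/FiO2);
- the table of confounders (comorbidities and pharmacotherapy);
- the regression list;
- the Information gathering instrument, whose 12 columns run from case to intubation.

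The protocol does accept that local circumstances matter. The Problem statement says that "mortality could be affected by medical practice in each region", and the Justification says "additionally there are mechanical ventilator deficits in most hospitals".

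**The concern.** The outcome is intubation for any cause, which is a treatment decision. Whether a patient is intubated can depend on the hospital's threshold and equipment, and whether a patient is proned can depend on the hospital's habits. A hospital characteristic that drives both is a confounder of exactly the relationship in the main objective. A pooled 2x2 table cannot separate it from an effect of proning, and the planned regression does not help because centre is not in it.

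The main hypothesis test could then reject the null of no relationship because of which hospitals contributed patients. Without a centre field, the study team could not check from the dataset whether this had happened, even descriptively.

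**Working it through.** **The protocol's own figure.** The sample size uses N = 8463, z = 1.96, p = q = 0.5, E = 0.05:

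n = N z² pq / [(N − 1)E² + z² pq] = 8127.87 / (21.155 + 0.9604) = 367.52, rounded up to 368.

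The stated 368 reproduces. It does not depend on centre, and serves below only as the study size.

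**Assumed inputs.** The protocol gives no number of centres and no centre-level proning or intubation rates. All such rates below are assumptions, and a range is shown.

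**Two types of centre, 184 patients in each, no prone effect within either.** Type A intubates 30% and type B 50%, proned or not.

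With proning at 80% in A and 20% in B:

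- risk if proned = 0.8 × 0.30 + 0.2 × 0.50 = 0.34
- risk if not proned = 0.2 × 0.30 + 0.8 × 0.50 = 0.46
- crude RR = 0.34 / 0.46 = 0.74, although the RR within each type is 1

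Rejection probability of the pooled test by normal approximation:

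- null SE = √(0.4 × 0.6 × 2/184) = 0.0511, so the critical difference is 1.96 × 0.0511 = 0.100
- actual SE = √(184 × (0.30 × 0.70 + 0.50 × 0.50)) / 184 = 0.050
- P(reject) ≈ Φ((0.12 − 0.100)/0.050) ≈ 0.65

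Simulation with 40,000 runs per row, pooled chi-square against Cochran-Mantel-Haenszel (CMH) stratified by centre:

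| Proning A / B | Intubation A / B | Crude RR | Pooled rejects | CMH rejects | Mantel-Haenszel RR |
|---|---|---|---|---|---|
| 80% / 20% | 30% / 50% | 0.74 | 65% | 5% | 1.00 |
| 70% / 30% | 30% / 50% | 0.82 | 34% | 5% | 1.00 |
| 70% / 30% | 35% / 45% | 0.90 | 12% | 5% | 1.00 |
| 60% / 40% | 30% / 50% | 0.90 | 11% | 5% | 1.00 |
| 50% / 50% | 30% / 50% | 1.00 | 4% | 5% | 1.00 |
| 80% / 20% | 40% / 40% | 1.00 | 5% | 5% | 1.00 |

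The last two rows show the condition: if either proning or intubation risk is equal across centres, the bias vanishes.

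**Ten centres, about 360 patients, no prone effect.** Centre log-odds vary at random for proning and intubation. Ranges cover separate runs of the simulation.

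| SD of log-odds (proning, intubation) | Correlation | Pooled rejects | Stratified rejects |
|---|---|---|---|
| 1.0, 0.7 | 0 | 11–12% | about 5% |
| 1.0, 0.7 | −0.5 | 25–27% | about 5% |
| half of each | 0 to −0.5 | about 5–8% | about 5% |

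**Precision cost of stratifying, in the 80/20 example.**

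- Crude: var(log RR) = 0.66/(184 × 0.34) + 0.54/(184 × 0.46) = 0.01055 + 0.00638 = 0.01693, SE 0.130.
- Stratified (Greenland-Robins variance at expected counts): each type has n₁n₀/n = 147.2 × 36.8 / 184 = 29.44. Then var = 29.44 × (0.21 + 0.25) / [29.44 × (0.30 + 0.50)]² = 13.542 / 554.70 = 0.02441, SE 0.156.
- Ratio 0.156 / 0.130 = 1.20, a 20% wider standard error even though no centre proned all or none of its patients.

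**The case against.** **Centre can still be recovered.** A reader might infer from the form that centre is lost for good. The documents do not support that. All variables come from the clinical file, each file sits in a hospital, and the case number may or may not carry a site code. What stands is that the protocol neither lists centre as a variable nor provides a stated field for it.

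**An analysis plan may adjust for centre.** One may exist and is not shown. But this protocol itself fixes the main test, the regression variables and the extraction form, and centre is in none of them. Followed as written, the analysis is unstratified.

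**The protocol's remarks do not establish centre differences.** This is right. The remark on regional practice concerns mortality in ventilated patients, and a ventilator shortage in most hospitals is not evidence that participating hospitals differ. That hospitals short of ventilators prone more and intubate less is a conjecture. The remarks make a centre effect plausible, no more.

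**The figures are assumed.** Also right. The 65% rests on an 80/20 split in proning. With modest variation across ten centres the pooled test rejects only about 5–8% of the time.

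**Centre is one confounder among several.** The crude table also ignores severity, comorbidities and pharmacotherapy, and the 2x2 comparison comes first, with a multivariable model to follow. This is a good reason to put centre in that model as well. It does not justify leaving centre out of both.

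**Conclusion.** The point stands as a conditional weakness that is cheap to repair. The study is multicentre and non-randomised, its main comparison is pooled, and centre is absent from every variable list and from the stated form fields. If centres differ in both prone use and intubation risk, that difference can appear as a prone effect.

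Under the assumed rates the consequence runs from negligible (about 5–8% false rejection with modest between-centre variation) to serious (crude RR 0.74 and about 65% rejection with no true effect). The true size and direction cannot be computed from the protocol.

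Two stronger readings should be avoided. The protocol does not show that any observed association would be a centre artefact; that needs both kinds of difference. Nor is the pooled p-value or interval always too optimistic when centre proning and intubation rates are uncorrelated. In that case rejection was 11–12% under the larger assumed variation, but about 5–6% at half of it.

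**What to change.** - Add a coded centre column to the Information gathering instrument, filled at extraction, and list centre as a variable.
- Report the number of centres, with prone use and intubation by centre.
- Make the main comparison a centre-stratified Mantel-Haenszel test, with a stratified relative risk and 95% CI. Keep the pooled 2x2 table as descriptive.
- Include centre in the multivariable model, as a fixed effect or random intercept. Severity, comorbidities and pharmacotherapy still have to be handled there, because stratifying by centre alone does not remove them.

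The cost at extraction is one column. The analysis cost is precision, and it grows with the difference in proning between centres: about 20% on the SE of log RR in the 80/20 example, less with smaller differences. Centres that proned all or none of their patients add nothing to the stratified estimate. This should be stated alongside the target of 368.
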